$$Y_{ijklm} = \mu + \tau_j + \varphi_k + \alpha_l + \gamma_m + \lambda_{lm} + \beta \cdot \text{baseline tTG IgA}_{ijklm} + \eta_i + \varepsilon_{ijklm}$$

where

Y_{ijklm} is the relative (%) change from baseline in anti-tTG IgA result for subject i ($i = 1, \dots, n_{jkl}$) from site j ($j = 1, 2, 3$), sex k ($k = 1, 2$) and treatment group l ($l = 1, 2, 3$) at visit m ($m = 3, 5, 7, 8$),

μ is the overall mean,

α_l is the fixed effect due to treatment l ,

φ_k is the fixed effect due to sex k ,

τ_j is the fixed effect due to site j ,

γ_m is the fixed effect due to time point m ,

λ_{lm} is the fixed interaction effect due to treatment l and time point m ,

β is the parameter estimate of the baseline anti-tTG IgA result,

η_i is the random effect due to subject i ,

ε_{ijklm} is the random error for subject i from site j ($j = 1, 2, 3$), sex k ($k = 1, 2$) and treatment group l for time point m .

Due to the repeated structure of the data, the measurements within a subject will be correlated. Therefore, it is assumed that the overall covariance matrix of the response is block-diagonal. In order to determine the covariance structure that best fits the data, the same model with different covariance structures is fitted. Initially, models will be fit

assuming unstructured (UN) variance-covariance structure. Common within and between treatment variance components (compound symmetry (CS), first-order autoregressive (AR(1)) and Toeplitz covariance structures) will be further explored to increase sensitivity of statistical tests. The best model will be chosen by comparing the Akaike Information Criterion (AIC) of the models with different covariance structures.

The following SAS program will be used for carrying out the analysis:

```
proc glimmix data=ttgiga;
  class subjid trt site sex time(ref=FIRST);
  model ttgiga = ttgiga.bl trt site sex time trt*time / solution;
  random _residual_ / subject=subjid type=UN;
  estimate "150 mg AMG 714 vs Placebo" trt 1 0 -1 /alpha=0.05 cl;
  estimate "300 mg AMG 714 vs Placebo" trt 0 1 -1 /alpha=0.05 cl;
  estimate "Visit 3: 150 mg AMG 714 vs Placebo" trt 1 0 -1
    trt*time 0 0 0 1
    0 0 0 0
    0 0 0 -1 /alpha=0.05 cl;
  estimate "Visit 3: 300 mg AMG 714 vs Placebo" trt 0 1 -1
    trt*time 0 0 0 0
    0 0 0 1
    0 0 0 -1 /alpha=0.05 cl;
  estimate "Visit 5: 150 mg AMG 714 vs Placebo" trt 1 0 -1
    trt*time 1 0 0 0
    0 0 0 0
    -1 0 0 0 /alpha=0.05 cl;
  ...

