The total weekly bowel movement counts will be analysed using generalized linear mixed models with subject as a random effect. The statistical model will include as fixed effects treatment group, sex, site, time (week) and time point-by-treatment group interaction. Poisson distribution with log-link will be used for modelling the counts. The following model will be fitted:

$$\log(Y_{ijklm}) = \mu + \tau_j + \varphi_k + \alpha_l + \gamma_m + \lambda_{lm} + \eta_i + \varepsilon_{ijklm},$$

where

Y_{ijklm} is the total bowel movement count for subject i ($i = 1, \dots, n_l$) from site j ($j = 1, 2, 3$), sex k ($k = 1, 2$) and treatment group l ($l = 1, 2, 3$) at visit m ($m = 3, 5, 7, 8$),

treatment group l ($l = 1, 2, 3$) at week m ($m = 0, 1, \dots, 16$),

μ is the overall mean on log-scale,

α_l is the fixed effect due to treatment l on log-scale,

φ_k is the fixed effect due to sex k on log-scale,

τ_j is the fixed effect due to site j on log-scale, γ_m is the fixed effect due to week m on log-scale,

λ_{lm} is the fixed interaction effect due to treatment l and week m on log-scale,

η_i is the random effect due to subject i ,

ε_{ijklm} is the random error for subject i from treatment group l for week m .

Due to the repeated structure of the data, the measurements within a subject will be correlated. Therefore, it is assumed that the overall covariance matrix of the response is block-diagonal. In order to determine the covariance structure that best fits the data, the same model with different covariance structures will be fitted. Initially, models will be fit assuming unstructured (UN) variance-covariance structure. Common within and between treatment variance components (compound symmetry (CS), first-order autoregressive (AR(1)) and Toeplitz covariance structures) will be further explored to increase sensitivity

of statistical tests. The best model will be chosen by comparing the Akaike Information Criterion (AIC) of the models with different covariance structures.

The following SAS code will be used to fit the above-specified model:

```

proc glimmix data=bsfs ic=q;
  class subjid trt sex site week(ref=FIRST);
  model bsfs = trt sex site week trt*week / solution dist=POISSON;
  random _residual_ / subject=subjid type=UN;
  estimate "150 mg AMG 714 vs Placebo" trt 1 0 -1 /alpha=0.05 cl ilink;
  estimate "300 mg AMG 714 vs Placebo" trt 0 1 -1 /alpha=0.05 cl ilink;
  estimate "Week 0: 150 mg AMG 714 vs Placebo" trt 1 0 -1

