7.7.4 Celiac Disease Patient Reported Outcome (CeD PRO)

The CeD PRO questionnaire was developed to assess symptom severity in clinical trials in subjects with celiac disease. Items in the questionnaire were formulated based on one-on-one interviews with patients with celiac disease, thus they reflect the symptoms that patients consider part of their celiac disease experience. The questionnaire is designed as a self-

administered daily diary, to be completed at the same time each day, and requires less than 10 minutes to complete. It includes nine items asking participants about the severity of celiac disease symptoms they may experience each day. Participants are asked to rate their symptom severity on an 11-point, 0 to 10 scale; from “not experiencing the symptom” to “the worst possible symptom experience”. Symptoms include abdominal cramping, abdominal pain, bloating, gas, diarrhoea, loose stool, nausea, headache and tiredness.

Subjects will be asked to maintain a daily e-diary for the CeD PRO instrument from baseline to final study visit.

The total CeD PRO score is calculated as the sum of scores of all nine questions in CeD PRO questionnaire. The smaller the total CeD PRO score, the milder the symptoms of the subject. For modelling purposes, the total CeD PRO score on weekly level is also calculated (the weekly total score is calculated as the mean of total daily scores of a given subject).

The CeD PRO will be analysed using a linear mixed effects repeated measures model (MMRM) with the baseline value, treatment group, site, sex, time point and a time point-by-treatment group interaction term as fixed effects with an underlying correlation structure between the time points that results in the best fit for the model. Subject will be included as a random effect.

Two separate models will be fitted: one for daily level data with time (days from baseline) as continuous variable and another for weekly level data with time (weeks from baseline) as a categorical variable.

For the daily level data, the following model will be fitted:

$$Y_{ijklm} = \mu + \alpha_j + \varphi_l + \tau_m + \beta \cdot \text{baseline CeD PRO}_{ij} + \gamma \cdot \text{day}_{ijklm} + \lambda_{jk} + \eta_i + \varepsilon_{ijklm}$$

where

Y_{ijklm} is the total CeD PRO score for subject i ($i = 1, \dots, n_j$) from treatment group j ($j = 1, 2, 3$), sex l ($l = 1, 2$) and site m ($m = 1, 2, 3$) at day k ($k = 0, 1, 2, \dots, 112$),

μ is the overall mean,

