α_j is the fixed effect due to treatment j ,

φ_l is the fixed effect due to sex l ,

τ_m is the fixed effect due to site m , β is the parameter estimate of the baseline total CeD PRO score,

γ is the parameter estimate of day,

λ_{jk} is the fixed interaction effect due to treatment j and day k ,

η_i is the random effect due to subject i ,

ε_{ijklm} is the random error for subject i from treatment group j , sex l and site m for day k .

Note that the proper functional form of the time (day) will be explored, e.g. square of day might be added.

The following SAS program will be used for carrying out the daily level analysis:

```

proc glimmix data=cedpro_d;
  class subjid trt site sex;
  model cedpro_d = cedpro_d_bl trt site sex day trt*day / solution;
  random _residual_ / subject=subjid type=AR(1);
  estimate "150 mg AMG 714 vs Placebo" trt 1 0 -1 /alpha=0.05 cl;
  estimate "300 mg AMG 714 vs Placebo" trt 0 1 -1 /alpha=0.05 cl;
  lsmeans trt /alpha=0.05 cl;
  ods output CovParms=Cov_Par LSMeans=LS_est Estimates=Eff_est
        FitStatistics=Fit_Stat ParameterEstimates=Par_est
        Tests3=Type_3;
run;

```

For the weekly level data, the following model will be fitted:

$$Y_{ijklm} = \mu + \alpha_j + \gamma_k + \lambda_{jk} + \beta \cdot baseline\ CeD\ PRO_{ijklm} + \eta_i + \varepsilon_{ijklm},$$

where

Y_{ijklm} is the total CeD PRO score for subject i ($i = 1, \dots, n_j$) from treatment group j ($j = 1, 2, 3$), sex l ($l = 1, 2$) and site m ($m = 1, 2, 3$) at week k ($k = 0, 1, \dots, 16$),
 μ is the overall mean,
 α_j is the fixed effect due to treatment j ,
 φ_l is the fixed effect due to sex l ,
 τ_m is the fixed effect due to site m ,
 γ_k is the fixed effect due to week k ,
 λ_{jk} is the fixed interaction effect due to treatment j and week k ,
 β is the parameter estimate of the baseline total CeD PRO score,
 η_i is the random effect due to subject i ,
 ε_{ijklm} is the random error for subject i from treatment group j , sex l and site m for week k .

The following SAS program will be used for carrying out the weekly level analysis:

```

proc glimmix data=cedpro_w;
  class subjid trt site sex week(ref=FIRST);
  model cedpro_w = cedpro_w_bl trt site sex week trt*week / solution;
  random _residual_ / subject=subjid type=AR(1);
  estimate "150 mg AMG 714 vs Placebo" trt 1 0 -1 /alpha=0.05 cl;
  estimate "300 mg AMG 714 vs Placebo" trt 0 1 -1 /alpha=0.05 cl;
  estimate "Week 0: 150 mg AMG 714 vs Placebo" trt 1 0 -1

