    trt*week 0 0 0 0 0 0 0 0 0 0 0 0 0 0 0 0 0 1
    0 0 0 0 0 0 0 0 0 0 0 0 0 0 0 0 0 0
    0 0 0 0 0 0 0 0 0 0 0 0 0 0 0 0 0 -1 /alpha=0.05 cl;
  estimate "Week 0: 300 mg AMG 714 vs Placebo" trt 0 1 -1
    trt*week 0 0 0 0 0 0 0 0 0 0 0 0 0 0 0 0 0 0
    0 0 0 0 0 0 0 0 0 0 0 0 0 0 0 0 0 1
    0 0 0 0 0 0 0 0 0 0 0 0 0 0 0 0 0 -1 /alpha=0.05 cl;
  estimate "Week 1: 150 mg AMG 714 vs Placebo" trt 1 0 -1
    trt*week 1 0 0 0 0 0 0 0 0 0 0 0 0 0 0 0 0 0
    0 0 0 0 0 0 0 0 0 0 0 0 0 0 0 0 0 0
    -1 0 0 0 0 0 0 0 0 0 0 0 0 0 0 0 0 0 /alpha=0.05 cl;

```

```
estimate "Week 16: 300 mg AMG 714 vs Placebo" trt 0 1 -1
        trt*week 0 0 0 0 0 0 0 0 0 0 0 0 0 0 0 0 0 0 0 0 0 0 0 0 0 0 0
        0 0 0 0 0 0 0 0 0 0 0 0 0 0 0 0 0 0 0 0 0 0 0 0 0 0 0 1 0
        0 0 0 0 0 0 0 0 0 0 0 0 0 0 0 0 0 0 0 0 0 0 0 0 0 0 0 -1 0 /alpha=0.05 cl;
lsmeans trt /alpha=0.05 cl;
lsmeans trt*week /alpha=0.05 cl;
ods output CovParms=Cov_Par LSMeans=LS_est Estimates=Eff_est
FitStatistics=Fit_Stat ParameterEstimates=Par_est
Tests3=Type_3;
run;
```

Due to the repeated structure of the data, the measurements within a subject will be correlated. Therefore, it is assumed that the overall covariance matrix of the response is block-diagonal (e.g. the observations between different subjects are not related, but the same correlation structure exists within subjects). In order to determine the covariance structure that best fits the data, the same model with different covariance structures is fitted. Initially, the models will be fitted assuming first-order autoregressive (AR(1)) variance-covariance structure. Common within and between treatment variance components (compound symmetry (CS), and Toeplitz covariance structures) will be further explored to increase sensitivity of statistical tests. The best model will be chosen by comparing the Akaike Information Criterion (AIC) of the models with different covariance structures.

Note that the value of `type` will be changed according to which covariance structure is being fitted.

The modelling results (parameter estimates, covariance parameter estimates, estimated treatment effect, marginal means estimates and results of the check of assumptions, e.g. the normality assumption) will be tabulated and 95% confidence intervals added, where appropriate. If the parametric assumptions are not met, then in addition to the above-specified model, a generalized estimating equation (GEE) approach will be used as well.

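### The repeated-measures models promise a random subject effect that the SAS code omits; if AIC selects AR(1) alone, standard errors of time-averaged contrasts and LS means are too small

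*SAP*

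**What the plan says.** SAP 7.7.4 (CeD PRO) states "Subject will be included as a random effect", and its daily and weekly equations carry a term η, which "is the random effect due to subject i", in addition to the error ε. Section 7.6.2 uses the same pattern for anti-tTG, anti-DGP, GSRS and CeD-GSRS. Weekly bowel movement counts (BSFS) are to be "analysed using generalized linear mixed models with subject as a random effect".

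The programs differ from this. Those in 7.6.2 use "random _residual_ / subject=subjid type=UN" and those in 7.7.4 use the statement beginning "random _residual_ / subject=subjid type=AR(1". No program contains a subject intercept. Between fits only the value of `type` changes.

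For CeD PRO the starting point is fixed: "Initially, the models will be fitted assuming first-order autoregressive (AR(1)) variance-covariance structure". The alternatives are "compound symmetry (CS), and Toeplitz covariance structures) will be further explored to increase sensitivity of statistical tests". Then: "The best model will be chosen by comparing the Akaike Information Criterion (AIC) of the models with different covariance structures". In 7.6.2 the start is UN, with CS, AR(1) and Toeplitz as further candidates.

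**The concern.** Text and code specify different models, and the SAP does not say which governs. Whether this matters depends on the structure chosen. UN, CS and Toeplitz allow a correlation that does not die out, so each can absorb a subject intercept. Under AR(1) alone the correlation decays to zero. Stable differences between subjects are then partly counted as independent information, and means over time look more precise than they are.

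AR(1) is a candidate for every repeated-measures endpoint and the starting structure for CeD PRO. Subject intercept plus AR(1), which is what the equation implies when the errors are AR(1), is never a candidate. At stake are the intervals for overall treatment contrasts and LS means of GSRS, CeD-GSRS and CeD PRO.

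**Working it through.** **Inputs.** 17 evaluable subjects per arm, 51 in total (SAP 6); two-sided 0.05 (7.2); 16 weekly points for GSRS and CeD-GSRS, 17 for weekly CeD PRO, 113 days for daily CeD PRO. The share of variance between subjects (ICC) and the AR correlation (ρ) are assumptions, because the SAP gives neither.

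**The plan's own figure.** The SAP states no operating characteristics for these models. Its only power figures are for the primary endpoint, and they reproduce: 40/(36·√(2/17)) = 3.239 and 35/(36·√(2/17)) = 2.834 as noncentrality parameters on 48 df give 88.76% and 79.32% (stated 88.8% and 79.3%).

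**Size of the SE error, weekly.** Let the truth have unit variance, a subject intercept with share ICC, and AR(1) errors with correlation ρ. The closest AR(1) has r = ICC + (1−ICC)ρ. The mean of T points under AR(1) has variance m(r) = (1/T)·[(1+r)/(1−r) − 2r(1−r^T)/(T(1−r)²)]. Take T = 16, ICC 0.2, ρ 0.5:
- r = 0.2 + 0.8·0.5 = 0.60, and m(0.60) = 0.2207. The AR(1) SE of an arm difference is √(0.2207·2/17) = 0.161.
- The true variance is 0.2 + 0.8·m(0.5) = 0.2 + 0.8·0.1719 = 0.3375, so the SE is 0.199.
- Ratio: 0.199/0.161 = 1.24.

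**When AIC would pick AR(1).** The expected gain in 2·log-likelihood of the true structure over the closest AR(1) is 51·[(T−1)ln(1−r²) − ln|V|]. Here ln|V| = T·ln(1−ICC) + (T−1)ln(1−ρ²) + ln(1 + q·ICC/(1−ICC)), with q = [T−(T−2)ρ]/(1+ρ). In the example this is 51·(−6.694 + 6.969) = 14.0. At 16 points Toeplitz has 14 more parameters than AR(1): a penalty of 28 less about 14 of expected overfit, so a net handicap near 14.

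**Weekly simulation.** Null data from the SAP's own equation; covariates baseline, sex and site; 16 points; REML; 1,500 data sets per setting. Contrast: overall 150 mg versus placebo.

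| ICC / ρ | AR(1) model SE / true SE | Error, AR(1) alone | Expected gain | AIC picks AR(1) | Error after selection | Error, intercept + AR(1) |
|---|---|---|---|---|---|---|
| 0 / 0.6 | 0.169 / 0.168 | 4.9% | 0 | 98% | 4.9% | 4.4% |
| 0.2 / 0.5 | 0.167 / 0.208 | 10.9% | 14.0 | 61% | 8.4% | 5.1% |
| 0.4 / 0.3 | 0.160 / 0.246 | 19.3% | 75.7 | 0% | 5.3% | 5.3% |
| 0.4 / 0.5 | 0.190 / 0.255 | 13.1% | 39.7 | 4% | 5.6% | 5.2% |
| 0.4 / 0.7 | 0.234 / 0.272 | 8.6% | 15.4 | 55% | 6.7% | 5.1% |
| 0.6 / 0.5 | 0.223 / 0.296 | 13.3% | 68.8 | 0% | 5.4% | 5.5% |
| 0.3 / 0.8 | 0.255 / 0.274 | 6.5% | 4.4 | 92% | 6.3% | 5.0% |

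The Monte Carlo SE is √(0.05·0.95/1500) = 0.56 points near 5%. Adding UN as a candidate changed none of the selected results. The last-week contrast under AR(1) had 4.7 to 5.5% error. With four visits (antibodies) the error after selection was at most 5.3%.

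**Daily CeD PRO.** Toeplitz has 113 parameters against 2, a net handicap of 222 − 111 = 111. The daily ESTIMATE has coefficients for treatment only, while day is continuous and interacts with treatment, so it compares arms at day 0. The LS means are at the mean day (56). With design X = (1, day), closest AR(1) covariance W and B = (X′W⁻¹X)⁻¹, the ratio of true to model SE is √(k′BX′W⁻¹VW⁻¹XBk / k′Bk). Here k = (1, 56) for the mean day and (1, 0) for day 0.

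| ICC / ρ | Expected gain (handicap 111) | Ratio, mean day | Ratio, day 0 |
|---|---|---|---|
| 0.2 / 0.5 | 260 | 2.53 | 1.46 |
| 0.4 / 0.5 | 574 | 2.94 | 1.61 |
| 0.4 / 0.7 | 278 | 2.28 | 1.32 |
| 0.2 / 0.8 | 62 | 1.67 | 1.13 |
| 0.3 / 0.8 | 108 | 1.82 | 1.16 |
| 0.4 / 0.9 | 57 | 1.48 | 1.04 |
| 0.2 / 0.9 | 20 | 1.34 | 1.03 |

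In 150 simulated data sets per setting (Toeplitz AIC approximated), AR(1) beat Toeplitz in 98 to 100% at 0.2/0.8 and 0.4/0.9, and in 0 to 2% at ρ 0.5 to 0.7. It beat CS in all of these runs.

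**The case against.** The strongest reply is that the AIC step already protects the analysis: where ignoring the subject effect does most damage, the likelihood gain is largest and Toeplitz wins. That stands. A reader might infer from the behaviour of AR(1) alone that daily standard errors are understated two- to threefold, or that weekly error approaches 19%. The documents do not support this, because those figures arise at settings where the SAP's own rule would rarely or never keep AR(1). They would apply only if Toeplitz failed to converge. The SAP names no fallback for that case, but nothing shows that it would occur.

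A reader might also take every contrast to be affected. Most weekly ESTIMATE statements are week-specific and stay near 5%, and the daily one is at day 0, where the understatement is small. The larger daily ratios concern arm LS means, which the code requests without differences.

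Section 7.6.1 lets code be modified without an amendment, so the repair is permitted. It does not say that text prevails over code, and 7.7.4 names only `type` as varying. The GEE in 7.7.4 is an addition if parametric assumptions fail, not a replacement. Finally, the endpoints concerned are secondary or exploratory.

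**Conclusion.** The contradiction between text and code is certain; its consequence is conditional and moderate.
- **Weekly models:** with between-subject variance present, AIC chose AR(1) in 0 to 92% of data sets. Type I error of the overall contrast after selection was about 5 to 8%, against 5.0 to 5.5% with the intercept.
- **Daily CeD PRO:** AR(1) is likely to survive only at ρ of about 0.8 to 0.9, or if Toeplitz does not converge. At that ρ the SE is understated about 1.5 to 1.8 fold for mean-day LS means (1.3 at ICC 0.2, ρ 0.9). For the coded day-0 contrast it is about 1.04 to 1.16 fold. By 2Φ(−1.96/ratio), the latter means roughly 6 to 9% error.
- **Hardly or not affected:** week-specific contrasts and the four-visit antibody models hardly; the primary ANCOVA not at all.

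These sizes rest on assumed ICC and ρ and on a truth of subject intercept plus AR(1). BSFS was not simulated. There the point is only that a random-subject Poisson model and a marginal residual-covariance model are different models.

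**What to change.** Before unblinding, state that the text governs and add `random intercept / subject=subjid;` beside the AR(1) residual statement in the weekly GSRS, CeD-GSRS and CeD PRO models and the daily CeD PRO model. Do not add it to UN or CS, where it is redundant. In a separate simulation of 300 data sets per setting, AIC chose intercept plus AR(1) in at least 94% when it was offered.

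For BSFS, decide between the random-subject model in the text and the marginal model in the code, make the two agree, and keep an allowance for over-dispersion.

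The cost is one code line in each linear model, some rewording for BSFS, and somewhat wider intervals. When no subject variance existed, the simulated weekly model SE was 0.173 with the intercept against 0.169 without, about 2% wider (0.173/0.169 = 1.02).

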7.2.1 Definition of derived variables

Geometric mean will be calculated as:

$$\text{mean}_{\text{geo}} = \sqrt[n]{x_1 x_2 \cdots x_n} = \exp\left\{\frac{1}{n} \sum_{i=1}^n \ln x_i\right\}.$$

Values that are missing or not available will be ignored in calculation of geometric mean.

CV%_{geo} will be calculated using the following formula:

$$\text{CV\%}_{\text{geo}} = 100\% \cdot \sqrt{\exp V_{\ln} - 1}.$$

Values that are missing or not available will be ignored in calculation of CV%_{geo}.

Absolute change from baseline for a given treatment needs to be calculated, the following formula will be used:

$$\text{Absolute change from baseline} = \text{Post-baseline value} - \text{Pre-dose value}.$$

For weekly scores, Week 0 score is considered to be the baseline value. If Week 0 score is not available, the first non-missing result within 2 weeks of treatment will be used as baseline. For daily scores (e.g. CeD PRO), Day 0 score is considered to be the baseline, in case Day 0 score is not available, the first non-missing result within 2 weeks of treatment will be used as baseline. Otherwise, the given subject will be considered non-evaluable for the specific test. In case pre-dose value doesn't exist (i.e. for biopsy endpoints), screening value will be used as baseline.

In the case where relative (%) change from baseline needs to be calculated, the following formula will be used:

$$\text{Relative (\%)} \text{ change from baseline} = (\text{Post-baseline value} - \text{Pre-dose value}) / (\text{Pre-dose value}) \cdot 100\%.$$

For weekly scores, Week 0 score is considered to be the baseline value. If Week 0 score is not available, the first non-missing result within 2 weeks of treatment will be used as baseline. For daily scores (e.g. CeD PRO), Day 0 score is considered to be the baseline, in case Day 0 score is not available, the first non-missing result within 2 weeks of treatment will be used as baseline. Otherwise, the given subject will be considered non-evaluable for the specific test. In case pre-dose value doesn't exist (i.e. for biopsy endpoints), screening value will be used as baseline.

Body mass index (BMI) is calculated using the formula:

$$\text{BMI (kg/m}^2\text{)} = \text{weight (kg)} / [\text{height (m)} * \text{height (m)}].$$

Body surface area (BSA) is calculated using Dubois' formula:

$$\text{BSA (m}^2\text{)} = 0.007184 * \text{height (cm)}^{0.725} * \text{weight (kg)}^{0.425}.$$

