Due to the repeated structure of the data, the measurements within a subject will be correlated. Therefore, it is assumed that the overall covariance matrix of the response is block-diagonal. In order to determine the covariance structure that best fits the data, the same model with different covariance structures is fitted. Initially, models will be fit assuming unstructured (UN) variance-covariance structure. Common within and between treatment variance components (compound symmetry (CS), first-order autoregressive (AR(1)) and Toeplitz covariance structures) will be further explored to increase sensitivity of statistical tests. The best model will be chosen by comparing the Akaike Information Criterion (AIC) of the models with different covariance structures.

The following SAS program will be used for carrying out the analysis:

```

proc glimmix data=gsrs;
  class subjid trt site sex week(ref=FIRST);
  model gsrs = gsrs_bl trt site sex week trt*week / solution;
  random _residual_ / subject=subjid type=UN;
  estimate "150 mg AMG 714 vs Placebo" trt 1 0 -1 /alpha=0.05 cl;
  estimate "300 mg AMG 714 vs Placebo" trt 0 1 -1 /alpha=0.05 cl;
  estimate "Week 1: 150 mg AMG 714 vs Placebo" trt 1 0 -1
    trt*week 0 0 0 0 0 0 0 0 0 0 0 0 0 0 0 0 1
    0 0 0 0 0 0 0 0 0 0 0 0 0 0 0 0 0
    0 0 0 0 0 0 0 0 0 0 0 0 0 0 0 0 -1 /alpha=0.05 cl;
  estimate "Week 1: 300 mg AMG 714 vs Placebo" trt 0 1 -1
    trt*week 0 0 0 0 0 0 0 0 0 0 0 0 0 0 0 0 0
    0 0 0 0 0 0 0 0 0 0 0 0 0 0 0 0 1
    0 0 0 0 0 0 0 0 0 0 0 0 0 0 0 0 -1 /alpha=0.05 cl;
  estimate "Week 2: 150 mg AMG 714 vs Placebo" trt 1 0 -1
    trt*week 1 0 0 0 0 0 0 0 0 0 0 0 0 0 0 0 0
    0 0 0 0 0 0 0 0 0 0 0 0 0 0 0 0 0
    -1 0 0 0 0 0 0 0 0 0 0 0 0 0 0 0 0 /alpha=0.05 cl;
  ...
  estimate "Week 16: 300 mg AMG 714 vs Placebo" trt 0 1 -1
    trt*week 0 0 0 0 0 0 0 0 0 0 0 0 0 0 0 0 0
    0 0 0 0 0 0 0 0 0 0 0 0 0 0 0 0 1 0
    0 0 0 0 0 0 0 0 0 0 0 0 0 0 0 0 -1 0 /alpha=0.05 cl;
  lsmeans trt /alpha=0.05 cl;
  lsmeans trt*week /alpha=0.05 cl;
  ods output CovParms=Cov_Par LSMeans=LS_est Estimates=Eff_est
    FitStatistics=Fit_Stat ParameterEstimates=Par_est
    Tests3=Type_3;
run;

```

Note that the value of `type` will be changed according to which covariance structure is being fitted.

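### The CeD PRO models enter the baseline score both as covariate and as a response row, and the daily model's overall contrast is really a Day 0 contrast

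*SAP*

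**What the plan says.** Section 7.2.1 defines baseline twice. First: "For weekly scores, Week 0 score is considered to be the baseline value". Second: "For daily scores (e.g. CeD PRO), Day 0 score is considered to be the baseline". If that score is missing, "the first non-missing result within 2 weeks of treatment will be used as baseline".

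Section 7.7.4 analyses the raw CeD PRO total, not a change score, in two models. The weekly score is the mean of the subject's daily totals. The weekly response runs "at week k ($k = 0, 1, \dots, 16" and the daily response "at day k ($k = 0, 1, 2, \dots, 112". Both models carry a baseline covariate; the weekly model statement is "model cedpro_w = cedpro_w_bl trt site sex week trt*week / solution". The weekly code then asks for treatment contrasts at Week 0 for both doses, for example "estimate 'Week 0: 150 mg AMG 714 vs Placebo' trt 1 0 -1". The diary starts at baseline, so the SAP offers no earlier run-in score as covariate.

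The other repeated-measures models with a baseline covariate (section 7.6.2) leave baseline out of the response. Anti-tTG and anti-DGP use Visits 3, 5, 7 and 8. GSRS and CeD-GSRS use Weeks 1 to 16, and their first time-specific contrast is "estimate 'Week 1: 150 mg AMG 714 vs Placebo' trt 1 0 -1". BSFS does include Week 0, but has no baseline covariate.

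**The concern.** When the baseline is also a response row, that row equals the covariate. The true slope there is 1, while later weeks have a smaller slope, yet the model fits one common slope. Three things follow in the weekly model:

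- A row that holds no treatment effect, if it is pre-dose, is averaged into the overall contrast.
- The slope used to adjust every later week is distorted.
- A Week 0 difference between arms is tabulated with a 95% confidence interval among the treatment effects.

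In the daily model day is continuous, so the meaning of the treatment main effect depends on where day equals zero.

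At stake are the size and labelling of an exploratory patient-reported result, which section 7.7.3 also lists as a candidate for the exposure-response work. No primary or secondary result is touched.

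**Working it through.** The SAP gives no figure on this point to reproduce.

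**Weekly model, overall contrast.** Inputs: 17 weeks (0 to 16) in section 7.7.4, categorical week, and `trt*week` in the model. A contrast on `trt` alone averages the 17 treatment-by-week cells equally. Let d_k be the expected effect in week k, with d_0 = 0 if Week 0 is pre-dose. With complete data:

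overall = (d_0 + d_1 + ... + d_16)/17 = (16/17) × mean(d_1, ..., d_16)

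16/17 = 0.941, a shrinkage of 1/17 = 5.9%. The factor does not depend on the shape of the effect over Weeks 1-16.

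**Weekly model, Week 0 contrast.** Let D be the difference in mean baseline between arms and b the fitted common slope. At Week 0 response and covariate coincide, so the fitted contrast is about D − bD = (1 − b)D. It contains no drug effect.

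**Simulation of the weekly model.** From the SAP: 17 evaluable subjects per arm (section 6). Assumed, not in the SAP: SD 10, effect −5 from Week 1, intercept plus AR(1) data, site and sex omitted. The model was an AR(1) fit by REML, with 400 runs per setting.

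| AR(1) correlation, subject variance share | Overall, Week 0 in | Overall, Week 0 out | Ratio | Slope in / out | Power in / out |
|---|---|---|---|---|---|
| 0.5, 0.3 | −4.54 | −4.82 | 0.941 | 0.42 / 0.37 | 0.83 / 0.83 |
| 0.7, 0 | −4.78 | −5.08 | 0.941 | 0.26 / 0.19 | 0.79 / 0.79 |
| 0.6, 0.5 | −4.80 | −5.10 | 0.942 | 0.61 / 0.57 | 0.86 / 0.85 |

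The standard error falls with the estimate (1.43 against 1.52, 1.74 against 1.82, 1.47 against 1.58), so power barely moves.

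The fitted slopes give 1 − b = 0.58, 0.74 and 0.39, so the Week 0 contrast shows roughly 39% to 74% of the chance imbalance. Over runs it averaged −0.04 to 0.13. Its model standard error (2.8 to 3.3) exceeded its actual spread (1.4 to 2.5), and it was significant in 0 to 1% of runs.

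**Daily model.** Day 0 is 1 of 113 days (0.9%). Because `day` is continuous, the estimate on `trt` alone gives `trt*day` a coefficient of zero and so evaluates the difference at Day 0. LSMEANS evaluates it at the mean day. Simulation used 150 runs per setting and the same SD. The constant effect was −5 from Day 1; the linear effect was −5 × day/56.

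| Effect; AR(1) correlation, subject share | LS-mean difference, Day 0 in / out | `trt` estimate, Day 0 in / out |
|---|---|---|
| Constant; 0.5, 0.3 | −4.70 / −4.80 | −4.47 / −4.85 |
| Constant; 0.8, 0 | −4.81 / −5.02 | −4.22 / −5.00 |
| Linear; 0.5, 0.3 | −4.82 / −4.86 | 0.24 / 0.23 |
| Linear; 0.8, 0 | −5.04 / −5.10 | 0.25 / 0.21 |

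The Day 0 row shrinks the LS-mean difference by about 2% and 4% (constant) and about 1% (linear). For a growing effect the estimate labelled as drug against placebo is near zero while the LS-mean difference is near −5, whether or not Day 0 is a response row.

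**The case against.** **Week 0 may not be pre-dose.** Section 3 labels the day after Visit 1 as Week 0/Day 1, and section 7.7.4 averages daily scores into weekly ones. Six doses every two weeks ending at Week 10 put the first dose at Week 0 (10 − 5 × 2 = 0). The Week 0 mean could therefore hold post-dose days. This stands: the 16/17 factor and the reading of the Week 0 contrast as pure imbalance are conditional on a pre-dose Week 0. A reader might infer that Week 0 certainly carries no treatment information; the SAP does not settle that. If it does hold post-dose days and is also the covariate, the covariate is partly post-treatment, which is no better.

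**Which baseline feeds the weekly model is unclear.** Section 7.2.1 gives Week 0 for weekly scores but names CeD PRO as its example of a daily score with a Day 0 baseline. If the weekly covariate were Day 0 alone and the Week 0 response a multi-day mean, the two would overlap without being identical. This also stands, and is a reason to define both.

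**The 6% is measured against the Weeks 1-16 average, which the SAP never names as its target.** That average includes the placebo-gluten weeks and the weeks after the challenge ends at Week 12. True, but adding a baseline week to the average serves no stated target either.

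**No inference changes.** This is largely right. A reader might infer false-positive findings or lost power. The calculations show neither: the overall test is almost the same and the Week 0 contrast rejects too rarely, not too often. Nor does the weekly 6% carry over to the daily model, where the Day 0 row costs about 1-4%.

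**Conclusion.** The double use of baseline is explicit in both CeD PRO models and departs from the SAP's other baseline-adjusted repeated-measures models. In the weekly model, given a pre-dose Week 0 and complete data, the overall estimate is 5.9% too small relative to Weeks 1-16, whatever the SD, the correlation or the shape of the effect. The slope distortion (0.04 to 0.07 upward) and the 39-74% share of imbalance depend on the assumed settings.

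In the daily model the Day 0 row matters little. The main fault there is that the treatment estimate is a Day 0 contrast; it can miss an effect that grows over time, and removing the Day 0 row does not repair it.

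Severity is low: the endpoint is exploratory and the overall weekly test is essentially unaffected.

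**What to change.** In sections 7.2.1 and 7.7.4:

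- Define the CeD PRO baseline for both models as the pre-dose Day 0 score, so that no post-dose day enters the covariate.
- Start the daily response at Day 1 and the weekly response at Week 1, with Week 1 as Days 1-7. Sixteen such weeks cover Days 1-112 exactly (16 × 7 = 112).
- Delete the two Week 0 estimate statements and rewrite the coefficient vectors for 16 weeks. The code makes the first week the reference and places it last, so Week 1 moves to the last position, as in the GSRS code.
- Where the two-week fallback makes a later score the baseline, drop that score from the response.
- Evaluate the daily treatment contrast at a stated day, or as an average over stated days, and label it so.

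The cost is small: new indices and definitions in the text, and edited code. Section 7.6.1 allows code changes without an amendment, but the equations and the baseline definition should be corrected too. No additional data are needed.
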